7.1.4 Exploratory endpoints

- Changes in exploratory biomarkers, which may include but are not necessarily limited to:
 - In blood only: microRNAs (miRs) other than miR-21

- In both blood and urine: β -2 microglobulin and CTGF
- In urine only: KIM-1 and calbindin-D28k
- Please see [Section 10.5.2.1.2](#) for study conduct in China.

7.1.5 Pharmacokinetic endpoint

- Plasma concentrations of lademirsen (SAR339375), RG0005, and SUM in C_{\max} samples and SUM only in C_{trough} samples.

7.2 STATISTICAL METHODS AND ANALYSES

The statistical analysis plan will be developed and finalized before database lock and will describe the subject populations to be included in the analyses. This section is a summary of the planned primary and secondary analyses.

7.2.1 Determination of sample size

An approximate 45 total subjects will be randomized in 2:1 ratio to lademirsen (SAR339375) versus placebo. The sample size will provide approximately 75% power to detect a reduced rate of decline of 5 mL/min/1.73 m²/year (~50% reduction) in eGFR annualized rate under lademirsen (SAR339375) treatment, in comparison to placebo.

Power calculations were based on simulations. The following model parameters were obtained from preliminary analysis of the ATHENA Natural History Study (OBS16374) data:

- Average linear decline in eGFR of 10 mL/min/1.73 m²/year in placebo arm
- Standard deviation (SD) for the residual error of eGFR of [REDACTED] mL/min/1.73 m² and SD for random effect of slope to be [REDACTED] mL/min/1.73 m²/year
- Mean and SD for intercept to be [REDACTED] mL/min/1.73 m² and [REDACTED] mL/min/1.73 m², respectively

In addition, power calculations were based on a success criterion defined in [Section 7.2.5](#) and a 10% dropout rate was assumed.

7.2.2 Analysis populations

The **Intent-to-Treat (ITT) Population** will consist of all randomized subjects analyzed according to the treatment group allocated by randomization. The ITT Population will be the primary efficacy analysis population.

The **Safety Population** will consist of all subjects who receive at least one dose or partial of a dose of the IMP, analyzed according to the treatment actually received.

The **PK Population** will consist of all subjects who receive at least one dose of the IMP and have at least one post-dose PK sample to determine plasma concentrations of lademirsen (SAR339375).

7.2.3 Demographic and baseline characteristics

Demographics will be presented using descriptive statistics (eg, mean, standard deviation, median, and range for continuous variables; number and percentage of subjects for categorical variables). No hypothesis tests will be performed on demographic and baseline characteristics.

7.2.4 Safety analysis

The summary of safety results will be presented by treatment group. All safety analyses will be performed on the Safety Population. The baseline value is defined generally as the last available value before randomization. The treatment-emergent adverse event (TEAE) period is defined as the time between the first administration of study medication to the last administration of study medication plus 10 weeks follow up.

Adverse events will be presented by System Organ Class (SOC) and Preferred Term (PT) for each treatment group, the number (n) and percentage (%) of subjects experiencing an AE. The numbers and percentages of subjects with at least one TEAE, treatment-emergent SAE, TEAE leading to death, and TEAE leading to permanent treatment discontinuation will be tabulated by treatment group. In addition, TEAEs will be described according to maximum intensity and relation to the study drug.

- The following deaths summaries will be generated
Death in nonrandomized subjects or randomized and not treated subjects
- Treatment-emergent AE leading to death (death as an outcome on the AE eCRF page as reported by the Investigator) by primary SOC, HLG, HLT, and PT showing number (%) of subjects sorted by internationally agreed order of SOC and alphabetic order of HLG, HLT, and PT
- ACSI will be summarized by treatment group

Results and change from baseline for the laboratory parameters will be summarized by treatment group for baseline and each post baseline time point, endpoint, minimum and maximum value. Summary statistics will include number of subjects, mean, standard deviation, median, Q1, Q3, minimum, and maximum.

The following definitions will be applied to laboratory parameters.

- The potentially clinically significant abnormality (PCSA) values are defined as abnormal values considered medically important by the Sponsor according to predefined criteria/thresholds based on literature review and defined by the Sponsor for clinical laboratory tests.

- PCSA criteria will determine which subjects had at least 1 PCSA during the on-treatment period, taking into account all evaluations performed during the on-treatment period, including unscheduled or repeated evaluations. The number of all such subjects will be the numerator for the on-treatment PCSA percentage.

The proportion of subjects who had at least one incidence of PCSA at any time during the TEAE period will be summarized by treatment group. Shift tables showing changes with respect to the baseline status will be provided. Vital signs, ECG and physical examinations will be summarized using descriptive statistics.

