- w* Serum chemistry will be done centrally except for exceptional circumstances, and urine pregnancy can be done locally.
- x* PK sampling time points on Day 1, Week 24 and Week 48 will be pre-dose (up to 4 hours before dose administration) and 4 hours post-dose. PK samples on other visits (Week 4, Week 12 and Week 36) will be pre-dose only (up to 4 hours before dose administration). No PK samples will be withdrawn on W4, W12, W24, W36, and W48, if injection is not administered and visit not performed. In case visit is performed (without injection administered), only pre-dose PK sample will be withdrawn. Time and date of PK sampling, as well as the date of the last prior administration of study drug should be recorded in the electronic case report form (eCRF).
- y* All ADA samples should be collected pre-dose (up to 4 hours before dose administration).
- z* Complement C3, C3a, C4, and Bb will be measured on Day 1 in samples obtained 0.5 hour pre-dose and 0.5, and 4 hours post-dose. On other visits, complement C3, C3A, c4, AND Bb will be measured pre-dose only.
- aa* Blood Urea Nitrogen, Albumin/creatinine ratio, urine Cystatin C: Urine Neutrophil Gelatinase Associated Lipocalin (NGAL), blood and urine transforming growth factor- β (TGF- β), and EGF see [Section 6.4](#) and [Section 10.5.2.2](#) (for study conduct in China). In addition Urine protein/creatinine ratio will be performed every 4 weeks, either using spot urine or 24h-h urine collection (at D1, W12, W24, W36, W48, and ET). In case of worsening of UPCR, the Investigator could repeat the UPCR before the next scheduled test.
- bb* May include but are not necessarily limited to the following: additional blood microRNAs, Kidney Injury Molecule-1, β -2 Microglobulin, and urine connective tissue growth factor (CTGF); and urine calbindin-D28k. For study conduct in China, see [Section 10.5.2.2](#).
- cc* Study drug administration and ISR assessment and reporting will be performed after each injection.
- dd* Subjects will be monitored for at least 2 hours after the first injection at baseline to ensure subject safety. In subsequent injections, the healthcare professional will monitor the subject's injection site for 15 minutes. The study staff will contact the subjects 1 day post injection to check on any occurrence of ISR and associated symptoms.
- ee* 12-lead ECG will be performed before IMP administration during the study treatment period.

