1.1.4.1 Study RG012-02

Safety, tolerability, and PK were evaluated in a Phase 1 study in which single ascending SC doses of lademirsen (0.5, 1.0, 2.0, 4.0, and 8.0 mg/kg) were administered to healthy adult subjects (males and females between 18 and 55 years of age). Pharmacokinetics of the parent compound (lademirsen [SAR339375]), its active metabolite (RG0005), and the sum of lademirsen (SAR339375) and RG0005 (SUM) were evaluated.

Lademirsen (SAR339375) was well tolerated, with an adverse event (AE) profile consistent with that anticipated for a second-generation oligonucleotide. All 40 subjects who enrolled successfully completed the study. There were no serious AEs or deaths, and all AEs were considered mild or moderate in severity.

The most commonly reported AEs in the overall study population were injection site events, with 183 events reported by 29 subjects (73%). Injection site AEs included erythema (63%), pain (63%), induration (28%), swelling (20%), hemorrhage (10%), and pruritus (10%). All injection site events resolved spontaneously or with minor intervention (eg, application of ice packs).

Other AEs that were reported in $\geq 5\%$ of subjects and more frequently reported in lademirsen (SAR339375)-treated subjects than placebo-treated subjects were abdominal pain (3 subjects [8%]), abdominal pain lower (2 [5%]), and back pain (2 [5%]).

There were no clinically important trends observed related to clinical laboratory, vital sign, electrocardiogram (ECG), or physical examination assessments.

PK results showed dose-dependent increases in plasma C_{max} (maximum concentration) and AUC (area under the concentration-time curve) consistent with the findings from nonclinical studies.

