5.3 OPEN-LABEL EXTENSION TREATMENT PERIOD

Subjects who complete the 48-week double-blind, placebo-controlled treatment period will be rolled over into the 48-week open-label extension period in which all subjects will receive active treatment with lademirsen (SAR339375) 110 mg QW. Subjects who complete the double-blind, placebo-controlled treatment period but who will not continue with the open-label extension will enter directly into the post-treatment follow-up period (see [Section 5.5](#)).

The open-label treatment period allows all the subjects to benefit from exposure to lademirsen (SAR339375) after the randomized period of the treatment. In addition, this allows us to gain long-term safety and efficacy data in Alport subjects. Procedures for study visits in the 48-week open-label extension will be nearly identical to those for the 48-week double-blind, placebo-controlled treatment period.

The following assessments, procedures, and data collection will be performed prior to dose administration, if not specify, at the study visits during the open-label extension treatment period:

Week 48 (±2 days) - Site Visit

The Week 48 visit of the double-blind, placebo-controlled treatment period will serve as the baseline visit of the open-label extension. Subjects continuing on to the open-label extension will receive their first open-label dose of lademirsen (SAR339375) at this visit. In addition to the procedures specified for this visit in [Section 5.2](#), vital signs will be taken both pre- and post-dose and AEs including information related to ISRs will be assessed for at least 2 hours after injection at Week 48.

Weeks: 49, 50, 51, 53, 54, 55, 57, 58, 59, 61, 62, 63, 65, 66, 67, 69, 70, 71, 73, 74, 75, 77, 78, 79, 81, 82, 83, 85, 86, 87, 89, 90, 91, 93, 94 and 95 (±2 days) - *Option for Alternative Location Visit

- CBC with differential
- Assessment of AEs including ISRs
- Injection of study drug

Week 52 (±2 days) - Site Visit

- Concomitant medications
- Vital signs and body weight
- Urinalysis
- Spot UPCR
- CBC with differential
- Coagulation panel
- Serum chemistry
- Lipid panel
- hs-CRP
- Urine pregnancy
- Assessment of AEs including ISRs
- Injection of study drug

Weeks: 56, 64, 68, 76, 80, 88, 92 (all ±2 days) - *Option for Alternative Location Visit

- Concomitant medications
- CBC with differential
- Urine pregnancy
- Spot UPCR
- Serum chemistry

- Coagulation panel
- Assessment of AEs including ISRs
- Injection of study drug

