4.7.1.1 Extent of investigational medicinal product exposure

The extent of IMP exposure will be assessed by the duration of IMP exposure and compliance, and actual dose information.

Duration of IMP exposure

Duration of IMP exposure in **placebo-controlled period**, will be summarized descriptively as a quantitative variable that number of participants, mean, SD, median, minimum, and maximum will be provided. In addition, duration of treatment exposure will also be summarized categorically by numbers and percentages for each of the following categories and cumulatively according to these categories: >0 and ≤12 weeks, >12 and ≤24 weeks, >24 and ≤36 weeks, ... (by every 12 weeks), and up to the last available study week during the defined treatment period.

Additionally, the cumulative duration of treatment exposure will be provided, defined as the sum of the duration of treatment exposure for all participants in placebo-controlled period, and will be expressed in patient years.

The duration of IMP exposure/cumulative duration of exposure **in lademirsen treatment period** and **in overall study period** will summarized similarly. The following categories of duration of treatment exposure will be presented: >0 and ≤12 weeks, >12 and ≤24 weeks, >24 and ≤36 weeks, ... (by every 12 weeks), and up to the last available study week during the defined treatment period.

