To notice that the AEs must happen within 7 days before or concomitant with the event of direct bilirubin >ULN during the same treatment emergent period. For example, if the event of direct bilirubin >ULN happened on October 1, 2021 00:00AM during the placebo-controlled treatment period, only if the mild Haemorrhage started between September 24, 2021 00:00AM (exclusion) to October 1, 2021 00:00AM (inclusion) during the placebo-controlled treatment period, it will be considered as meeting the criteria of Grade 3 direct bilirubin during the placebo-controlled treatment period.

The **primary focus** of adverse event reporting will be on double blind period in placebo-controlled treatment-emergent events on the safety population unless otherwise specified. Key adverse events will also be summarized for the lademirsen treated population in lademirsen treatment period.

Generalities

If an adverse event date/time of onset (occurrence, worsening, or becoming serious) is incomplete, an imputation algorithm will be used to classify the adverse event as pre-treatment and treatment-emergent periods. The algorithm for imputing date/time of onset will be conservative and will classify an adverse event as treatment emergent unless there is definitive information to determine it is not on treatment emergent periods. Details on classification of adverse events with missing or partial onset dates are provided in [Section 5.3](#).

Adverse event incidence tables will present by SOC, and PT, sorted by internationally agreed order of primary SOC and by decreasing incidence of PTs within each SOC, the number (n) and percentage (%) of participants experiencing an adverse event. Multiple occurrences of the same event in the same participant will be counted only once in the tables within a treatment phase. The denominator for computation of percentages is the defined population (eg, safety population, lademirsen treated population) within each treatment group. Sorting will be based on results of the lademirsen group if the analysis is on DB TE period or the overall group if the analysis is on lademirsen TE period.

Analysis of all treatment-emergent adverse events

- Overview of treatment-emergent adverse events, summarizing number (%) of participants with any
 - Treatment-emergent adverse event,
 - Serious treatment-emergent adverse event,
 - Treatment-emergent adverse event leading to death,
 - Treatment-emergent adverse event leading to dose reduction, and

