- All treatment-emergent adverse events leading to dose reduction in placebo-control treatment period showing the number (%) of participants with dose reduction due to treatment-emergent adverse event sorted by internationally agreed order of primary SOC and by decreasing incidence of PTs within each SOC will be presented.
- TEAE leading to dose reduction will be indicated in the listing of TEAEs.

Analysis of all treatment-emergent adverse events of special interest (AESI)

- All treatment-emergent AESIs identified by investigator (eg, through eCRF) in placebo-control treatment period showing the number (%) of participants by PT, sorted by the decreasing incidence of PT will be presented.
- AESIs identified by investigator will be indicated in the listing of TEAEs.

Analysis of treatment-emergent injection site reaction (ISR)

- Number (%) of participants with treatment emergent injection site reactions by PT by grade/maximal intensity will be provided.

Note: If more than one ISR records (eg, when the ISR grading is \geq None [Grade 0]) corresponding to the same adverse event (eg, when the AE code is same) as collected in eCRF, they will be considered as one ISR adverse event during the analysis.

Analysis of post-treatment adverse events

- A listing of all adverse events during the post-treatment period may be presented.

Deaths

- A listing of all adverse events leading to death during the study will be presented if any.

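### AE and injection site reaction tables count participants only, so the frequency and time course of reactions go unreported and lademirsen-period percentages rest on very unequal exposure

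*Protocol*

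**What the plan says.** **Counting unit.** Protocol 7.2.4 presents AEs by treatment group as "the number (n) and percentage (%) of subjects experiencing an AE". SAP 4.7.2 (Generalities) adds: "Multiple occurrences of the same event in the same participant will be counted only once in the tables within a treatment phase".

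**ISRs.** The one ISR summary in SAP 4.7.2 reads: "Number (%) of participants with treatment emergent injection site reactions by PT by grade/maximal intensity will be provided". A note beneath it treats several ISR records under the same AE code as one ISR adverse event.

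**How often ISRs are assessed.** Protocol Table 1, footnote cc: "Study drug administration and ISR assessment and reporting will be performed after each injection". Dosing is weekly. On the Week 48 visit, Protocol 5.3 says: "Subjects continuing on to the open-label extension will receive their first open-label dose of lademirsen (SAR339375) at this visit". The double-blind doses therefore fall at Weeks 0 to 47, at most 48 injections.

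**Exposure.** SAP 4.7.1.1 calculates cumulative exposure, "defined as the sum of the duration of treatment exposure for all participants in placebo-controlled period, and will be expressed in patient years", and does the same for the lademirsen treatment period. These patient-years appear only in the exposure summary; no AE table uses them as a denominator.

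**Periods.** SAP 4.7.2 puts the main focus of AE reporting on the double-blind period. SAP 4.8.5 summarises categorical safety data during lademirsen exposure as one overall group. Section 3 of the SAP addendum lets limited key safety analyses run to 96 weeks of lademirsen treatment. It also records that the study ended before all Stage 1 participants had finished the double-blind period.

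**The concern.** Safety and tolerability is a primary objective of the approved protocol (2.1), and Protocol 1.3.1 names ISRs as one of two important identified risks. The trial collects an ISR assessment after every injection and then reduces each participant to yes or no, with a worst grade. A participant with one mild reaction and a participant with 48 mild reactions fall in the same cell. The summary cannot say what proportion of injections cause a reaction, or whether reactions lessen or build up. Those are the questions a prescriber or patient would ask about a weekly injection.

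The AE percentages for the lademirsen period raise a different problem. Participants randomised to lademirsen can contribute up to 96 weeks and those who switch from placebo up to 48, and early termination cut both short by varying amounts. A crude percentage over such a mixture is not a risk at any stated time.

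**Working it through.** **Step 1. Reproduce the stated figure.** Protocol 1.1.4.1 gives 29 subjects with injection site events among 40 in the single-dose study RG012-02. 29/40 = 72.5%, stated as 73%. Protocol 10.5.1.1.2 gives mild 43% and moderate 30% for that study. 43 + 30 = 73, so the severity classes appear exclusive.

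**Step 2. Nearest prior data.** RG012-05 gave five weekly doses to 24 subjects randomised 3:1 (Protocol 1.1.4.2). It had mild ISRs in 46% and moderate in 21% (10.5.1.1.2). If exclusive, any ISR is 46 + 21 = 67%, or 16/24; moderate is 5/24. In PDY16327 all 4 Alport patients had ISRs.

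**Step 3. Project to 48 injections.** With independent injections, P(any in n) = 1 − (1 − p)^n.
- Any ISR: p = 1 − (1 − 16/24)^(1/5) = 0.197, so 1 − 0.803^48 is above 99.9%.
- Moderate ISR: p = 1 − (1 − 5/24)^(1/5) = 0.0456, so 1 − 0.9544^48 = 89%.

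With clustering within subjects, use a beta-binomial: P(any in n) = 1 − B(a, b+n)/B(a, b), with a = ms, b = (1−m)s, s = 1/ρ − 1. The mean m is set so that n = 5 returns the RG012-05 figure. The within-subject correlation ρ is an assumption, because the documents do not give it.

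| ρ | Any ISR: mean p per injection | Mean injections with an ISR (48 × p) | Any ISR at 48 | Moderate ISR at 48 |
|---|---|---|---|---|
| 0 | 0.197 | 9.5 | >99.9% | 89% |
| 0.1 | 0.237 | 11.4 | 98.6% | 61% |
| 0.3 | 0.318 | 15.3 | 92.7% | 44% |
| 0.5 | 0.410 | 19.7 | 86.5% | 36% |
| 0.7 | 0.513 | 24.6 | 79.9% | 30% |

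Every row fits the same five-dose result. Down the table the mean number of injections with a reaction rises from 9.5 to 24.6, while the any-ISR percentage falls from over 99.9% to 80%. The participant percentage is therefore a poor guide to burden and can even move in the opposite direction.

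**Step 4. Sensitivity to a lower rate.** With independent injections, p = 1%, 2%, 5% and 8% gives 38%, 62%, 91% and 98% at 48 injections. Saturation needs roughly 8% or more per injection and weak clustering.

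**Step 5. Unequal exposure, no drug effect.** Protocol 7.2.1: "An approximate 45 total subjects will be randomized in 2:1 ratio to lademirsen (SAR339375) versus placebo", so about 30 and 15 (SAP 1.1 records 43 in Stage 1). Assume a constant hazard and full follow-up. Then q96 = 1 − (1 − q48)² and the lademirsen-period percentage is (30·q96 + 15·q48)/45.

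| 48-week incidence | 96-week incidence | Lademirsen-period percentage | Ratio to 48-week |
|---|---|---|---|
| 5% | 9.8% | 8.2% | 1.63 |
| 10% | 19% | 16% | 1.60 |
| 20% | 36% | 30.7% | 1.53 |
| 30% | 51% | 44% | 1.47 |

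Full follow-up would give 30×96 + 15×48 = 3,600 person-weeks on lademirsen against 15×48 = 720 on placebo. Early termination makes the real mix shorter and less even, so these ratios illustrate the effect and are not forecasts.

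**Step 6. Early stopping in the double-blind period.** Take h = −ln(0.70)/48 per week, and suppose stoppers contribute 17 weeks (a stop near Week 16 plus the 7-day window in SAP 4.1), a risk of 1 − exp(−17h) = 11.9%. If 20% of active participants stop then, 0.8×30% + 0.2×11.9% = 26.4% against 30% on placebo. At 10%, matching the size of the protocol's dropout assumption, it is 28%. Even at 20% the shift is about one participant in 30 (7.9 against 9.0).

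**The case against.** The case against is substantial, and much of it stands.

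- A reader might infer that the ISR table will read about 100% in both arms and so hide any difference. The documents do not support this. The table is split by preferred term and maximal grade. In RG012-02 the individual terms ran from 63% down to 10%, and moderate-grade rows need not saturate. No placebo ISR rate is given, so a ceiling on placebo is not shown. The healthy-volunteer percentages appear to include placebo subjects, and RG012-02 used doses from 0.5 to 8 mg/kg.
- A reader might also infer that the plan compares pooled lademirsen percentages with 48-week placebo. It does not. The double-blind table, with the same window rule in both arms (SAP 4.1), is the primary safety comparison. The lademirsen period has no placebo column, and the addendum reports the two periods separately.
- Other outputs bear on tolerability: a listing of all TEAEs, dose reductions by 12-week block, counts of omitted doses, and TEAEs leading to dose reduction or discontinuation.
- Safety is descriptive, so a between-arm test of ISR rates would not fit the plan.

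These points limit the claim but do not remove the gap. Worst grade is not frequency, a listing is not a summary, and none of the other outputs gives reactions per injection or a rate over time at risk.

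**Conclusion.** The point holds as a gap in the summary measures. For a repeated, identified risk assessed after every injection, the plan reports whether a reaction occurred and its worst grade, but not how often or when. On the RG012-05 figures, any-ISR incidence on lademirsen is plausibly about 80% to over 99.9%, and moderate-ISR incidence about 30% to 89%. This rests on the mild and moderate classes being exclusive, on a constant per-injection rate, on an assumed correlation of 0 to 0.7, and on all 48 injections being given. Dose reductions, omitted doses and early termination would lower that count.

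The lademirsen-period AE percentages have no defined time horizon. In the illustration, longer follow-up alone lifts them about 1.5 to 1.6 times for events with 5% to 30% incidence at 48 weeks. This is a limit on interpretation, not an error in a planned comparison. The change is a worthwhile, cheap improvement and does not call the primary safety table into question.

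**What to change.** In SAP 4.7.2, carried into the addendum, keep every n (%) table and add two descriptive summaries.

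1. **ISR frequency.** Report injections with at least one ISR per 100 injections given, by arm, by Table 6 grade and by 12-week block. Count from the per-injection ISR records (Grade 1 or higher), not from the merged ISR adverse events. Use injections actually administered as the denominator, so that omitted doses and reduced schedules are handled correctly.
2. **Exposure-adjusted incidence.** For TEAEs, SAEs, AESIs and TEAEs leading to permanent discontinuation, report participants with a first event divided by time at risk, per 100 patient-years. Do this for the placebo-controlled and the lademirsen treatment periods, within the windows in SAP 4.1. Time at risk stops at the first event, so it is not identical to the cumulative exposure in SAP 4.7.1.1 but uses the same dates.

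No between-arm test is needed. The cost is a few extra summary tables and one extra counting rule for ISRs. No new data or protocol change is required.
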